- l Digital and paper ECGs will be performed predose and at 1.5, 6, and 24 hours postdose.
- m Telemetry to be performed for 4 hours on Day -1 during Period 1 only. For each period, telemetry will occur approximately 30 minutes predose until 24 hours postdose.
- n Additional cardiac blood biomarkers may be collected along with an ad hoc echocardiogram on occurrence of cardiac AE.
- o Randomization will occur in Dosing Period 1 on Day 1, predose only.
- p Subjects will receive a single dose on Day 1 of Dosing Periods 1, 2, 3, and 4 according to their randomized treatment sequence.
- q Plasma samples will be collected predose and 0.5, 1, 1.5, 2, 4, 6, 8, 12, 24, and 36 hours postdose on Dosing Periods 1, 2, 3, and 4.
- r Period 1 only.

BMI body mass index; HIV human immunodeficiency virus; SAE serious AE.

Table 3 Detailed study plan for Day 1 of Dosing Periods 1, 2, 3, and 4

t (hours)	PK blood collection	dECG	Supine blood pressure	Troponin, BNP, CPK, and CK-MB
0	X	X	X	X
0.5	X			
1	X			
1.5	X	X	X	
2	X			
4	X			
6	X	X	X	X
8	X			
12	X			
24	X	X	X	
36	X			

Table 4 Time schedule for digital ECG (dECG) assessments during residential period

Study Days	ECG Number	Time: Start hour: minute ^a	Dose	Time: Stop hour: minute	dECG continuous ^{bcd}	Other
1		-01:30		-01:00		Apply the electrodes ^c
1		-00:40		-00:30		Rest in bed
1	1	-00:30	Predose	-00:20	10 minutes	
1		-00:20		-00:05		Toilet use recommended
1		00:00	Admin of AZD6244/ placebo			
1	2	01:25		01:30	5 minutes ^d	
1	3	05:55		06:00	5 minutes ^d	
2	4	23:55		24:00	5 minutes ^d	

^a Time points for dECG may be adjusted according to emerging PK data.

^b The subject must be in the same supine body position (maximum 30 degrees flexion in the hip) at each time point and at all visits. Subject's feet should not contact the footboard of the bed.

^c Skin must be cleaned, and electrode positions marked with an indelible pen. Electrodes should be applied at least 30 minutes before first recording.

^d Subject must rest in bed for at least 10 minutes prior to each ECG time point.

Admin administration; dECG digital electrocardiogram; ECG electrocardiogram; PK pharmacokinetic.

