For SAEs causal relationship will also be assessed for other medication and study procedures and additional study medication. Note that for SAEs that could be associated with any study procedure the causal relationship is implied as ‘yes’.

A guide to the interpretation of the causality question is found in [Appendix B](#) to this CSP.

Adverse events based on signs and symptoms

All AEs spontaneously reported by the volunteer or reported in response to the open question from the study personnel: ‘Have you had any health problems since the previous visit/you were last asked?’, or revealed by observation will be collected and recorded in the eCRF. When collecting AEs, the recording of diagnoses is preferred (when possible) to recording a list of signs and symptoms. However, if a diagnosis is known and there are other signs or symptoms that are not generally part of the diagnosis, the diagnosis and each sign or symptom will be recorded separately.

Adverse events based on examinations and tests

The results from CSP-mandated laboratory tests and vital signs will be summarized in the CSR. Deterioration as compared to baseline in CSP-mandated laboratory values, vital signs, or ECGs should therefore only be reported as AEs if they fulfill any of the SAE criteria or are the reason for discontinuation of treatment with the IP.

If deterioration in a laboratory value/vital sign/ECG is associated with clinical signs and symptoms, the sign or symptom will be reported as an AE and the associated laboratory result/vital sign/ECG will be considered as additional information. Wherever possible the reporting Investigator will use the clinical, rather than the laboratory term (eg, anemia versus

low hemoglobin value). In the absence of clinical signs or symptoms, clinically relevant deteriorations in nonmandated parameters should be reported as AE(s).

Any new or aggravated clinically relevant abnormal medical finding at a physical examination as compared with the baseline assessment will be reported as an AE.

The aspartate aminotransferase or ALT 3 or more times the upper limit of normal (ULN) **and** total bilirubin (TBL) 2 or more times the ULN at any point during the study irrespective of an increase in alkaline phosphatase (ALP). The elevations do not have to occur at the same time or within a specified time frame. Please refer to [Appendix D](#) 'Hy's Law', for further instructions.

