6.3.8 Electrocardiogram

6.3.8.1 Resting 12-lead pECG

A 12-lead resting pECG will be performed on the days indicated in the study plan (Table 2). Volunteers must rest in a supine position for 10 minutes before each assessment. Overall evaluation (normal/abnormal) will be recorded in the eCRF. If the pECG is abnormal, the abnormality and its clinical significance will be specified in the eCRF. The print-out of the pECG is to be signed, dated, and filed in the Investigator's Study File along with a signed and dated copy (if the print-outs are not on archive-quality paper).

For AEs based on examinations and tests, see Section 6.3.3.

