Finally, an external expert cardiologist will review the totality of data and perform all necessary adjustments before locking the EClysis[®] data into a read-only state.

The numerical values for ECG intervals and amplitudes will be exported and made accessible on the AstraZeneca central dECG repository to accredited data management specialists for conversion into SAS files.

The following variables will be reported by the AstraZeneca ECG Centre: RR, PR, QRS, and QT intervals from the lead defined as primary in the protocol. Derived parameters (QTcF, HR, and others, as applicable) are calculated by the study statistician or designee.

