11.1.2 Other significant adverse events (OAE)

During the evaluation of the AE data, an AstraZeneca medically qualified expert will review the list of AEs that were not reported as SAEs and discontinuations due to AEs (DAEs). Based on the expert's judgment, significant AEs of particular clinical importance may, after consultation with the Global Patient Safety Physician, be considered other significant AEs (OAEs) and reported as such in the CSR. A similar review of laboratory/vital signs data will be performed for identification of OAEs.

Examples of these are marked hematological and other laboratory abnormalities, and certain events that lead to intervention (other than those already classified as serious), dose reduction, or significant additional treatment.

Any abnormal deviation in ECG intervals, amplitude, or morphology that is associated with symptoms is to be reported as an AE.

Any abnormal deviation in ECG/telemetry intervals, amplitudes, or morphology that is deemed to require a change in patient care, surveillance, or study participation is to be reported as an AE/DAE.

Any asymptomatic deviation in ECG/telemetry intervals, amplitudes, or morphology that is deemed not to constitute a safety concern for the individual volunteer, nor to require a change in volunteer care, surveillance, or study participation is to be reported qualitatively as an outlier value or with a narrative in the CSR. This includes also eg, short, asymptomatic, accidentally found paroxysmal supraventricular tachycardia or nonsustained ventricular tachycardia with characteristics that are normally not associated with test drug exposure:

Extra measurements (such as unscheduled or repeat assessments) will not be included in the descriptive statistics, but will be included in data listings. All AEs, ECG outliers for QTcF (ie, greater than 450, greater than 480, greater than 500 ms, or change from baseline greater than 30 and greater than 60 ms) and clinical laboratory outliers that occur following the first dose of IP will be included in the tabulations of AEs and outlier events, including episodes that occur at unscheduled evaluations or during the washout period between treatments.

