12.2.4 Safety and tolerability

All safety data (scheduled and unscheduled) will be presented in the data listings. Continuous variables (hematology, clinical chemistry, dECGs, and vital signs) will be summarized using descriptive statistics (n, mean, SD, minimum, median, and maximum) by treatment or scheduled time point, as appropriate. Categorical variables (eg, urinalysis, etc) will be summarized in frequency tables (frequency and proportion) by treatment group or scheduled time point, as appropriate. Where applicable, data will be summarized for the absolute value at each scheduled assessment, and for the corresponding change from baseline. Adverse events will be summarized in frequency tables (frequency and proportion) for each treatment. Graphical presentations may be used, as appropriate.

All AEs will be collected for each volunteer from Day -1 until the follow-up visit. Adverse events that occur before the first dose of IP will be listed only. On-treatment AEs (ie, those beginning after the first dose of IP) will be summarized by preferred term and system organ class using MedDRA vocabulary with volunteer counts and percentages and also by severity and casualty. Furthermore, listings of deaths (if any), SAEs, and AEs that lead to study discontinuation will be made. The number of volunteers who have any AEs, SAEs, AEs that lead to withdrawal, AEs of different intensity, and AEs judged causally related to IP by the Investigator will be summarized.

For clinical laboratory tests, listings of values for each volunteer will be presented with abnormal or out-of-range values flagged. Clinical laboratory data will be reported in Système International units in the CSR. Shifts in clinical laboratory data will be tabulated.

Results from the physical examinations, pECGs, echocardiograms, and eye examinations will be presented in listings only.

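### An asymptomatic, non-serious change on a scheduled ECG that needs closer surveillance while dosing continues is not an AE under Section 6.3.3 but is one under Section 11.1.2

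*Protocol*

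**What the plan says.** Section 6.3.3 (adverse events based on examinations and tests) covers deterioration from baseline in laboratory values, vital signs and ECGs that the protocol mandates. Such changes "should therefore only be reported as AEs if they fulfill any of the SAE criteria or are the reason for discontinuation of treatment" with the investigational product (IP). For findings without symptoms, the section adds AE reporting only for parameters that the protocol does not mandate.

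Section 11.1.2 has its own rules for ECG and telemetry findings. A symptomatic deviation is an AE. A deviation "deemed to require a change in patient care, surveillance, or study participation is to be reported as an AE/DAE". An asymptomatic deviation that raises no safety concern and needs no such change is handled as an outlier value or a narrative.

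The ECGs are mandated. Under Table 2 in Section 3.1, "Digital and paper ECGs will be performed predose and at 1.5, 6, and 24 hours postdose". Section 6.3.8.1, on the paper ECG, gives the site one pointer: "For AEs based on examinations and tests, see Section 6.3.3".

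On reporting, Section 12.2.4 states: "Adverse events will be summarized in frequency tables (frequency and proportion) for each treatment". It also states: "Results from the physical examinations, pECGs, echocardiograms, and eye examinations will be presented in listings only". For the digital ECG, Section 6.3.8.2 names as reported variables the "RR, PR, QRS, and QT intervals from the lead defined as primary in the protocol", with derived values such as QTcF and heart rate.

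**The concern.** Two instructions in one protocol classify the same finding in opposite ways, and the site makes the classification when it fills in the eCRF. An analysis plan cannot tabulate as an AE something the site was told not to record as one.

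Safety and tolerability is a secondary objective, and the AE tables by treatment are its main summary. If the site follows the pointer in 6.3.8.1, the finding does not reach those tables, although 11.1.2 requires it to be reported as an AE. The label may also have a clinical consequence, because Section 3.2 attaches mandatory action to a cardiac AE and does not define that term.

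**Working it through.** No arithmetic applies. The check is to put one case through both rules: a change on a scheduled ECG, without symptoms, meeting no SAE criterion, not a reason to stop IP, and judged to need closer surveillance.

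**Section 6.3.3**
1. Is the test mandated? Yes, by Table 2, so the restrictive sentence applies.
2. Is an SAE criterion met? No.
3. Is it the reason for stopping IP? No.
4. Are there symptoms that would be the AE in their own right? No.
5. Does the provision for asymptomatic findings help? No, it covers non-mandated parameters only.

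Result: not an AE.

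**Section 11.1.2**
1. Is it an abnormal ECG deviation? Yes.
2. Does it need a change in care, surveillance or participation? Yes, surveillance.
3. Is it in the asymptomatic tier left out of AE reporting? No, because that tier requires that no such change is needed.

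Result: an AE.

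**Readings that might reconcile the two**
- *The AE/DAE wording means discontinuations only.* It does not, because care and surveillance are listed separately from study participation.
- *The general AE definition in 6.3.1 settles it.* That definition admits abnormal ECGs, but 6.3.3 then narrows it for mandated tests.
- *The finding is serious anyway.* Some are. The important-medical-event criterion in 6.3.2 and Appendix B captures changes that may need intervention to prevent a serious outcome, and both sections then agree. This removes many changes in care and leaves mainly surveillance-only findings.
- *Section 3.2 settles it.* It does not; the outcome depends on which rule is applied first. Starting from 6.3.3, the finding is not an AE, so it is not a cardiac AE, dosing continues, and it remains a non-AE. Starting from 11.1.2, it is an AE. If that AE counts as cardiac, Section 3.2 requires withdrawal, the finding becomes the reason for stopping IP, and 6.3.3 then also makes it an AE. Each path is consistent with itself.

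**Where an unrecorded finding would still appear**
- An interval change appears in the digital-ECG summaries and, for QTcF, in the categorical tables of Section 12.2.4.
- A rhythm or morphology change appears in the eCRF, where 6.3.8.1 requires the abnormality and its clinical significance, and in the paper-ECG listing. It appears in no by-treatment table that the protocol names.

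**The case against.** The best answer is that the specific rule governs the general one. Section 6.3.3 is a general recommendation covering three kinds of test. Its reason is that mandated laboratory and vital-sign results will be summarized in the study report anyway, and that reason does not mention ECGs. Section 11.1.2 is specific to ECG and telemetry, is worded more firmly and sets out a complete scheme. A careful reader could well apply it. This softens the conflict without removing it: the protocol does not state this order, 11.1.2 is not worded as an exception to 6.3.3, it sits in a chapter on evaluating variables, and the section used by the site points the other way.

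The second answer is that little is lost. Paper-ECG abnormalities are recorded and listed, digital ECGs are taken at the same Day 1 times, an external cardiologist reviews the digital data, and with at most 30 volunteers the listings can be read directly. This stands and limits the weight of the point.

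The third answer is that aligning 6.3.3 with 11.1.2 might do more than relabel. If the resulting AE is read as a cardiac AE, Section 3.2 calls for an echocardiogram and a further biomarker sample, and requires cardiologist referral and withdrawal. Section 5.9 says withdrawn volunteers are not replaced, so pharmacokinetic periods could be lost. This also stands. It is why 6.3.3 should not be changed without a statement in 3.2. The exposure is not created by the fix, since a site following 11.1.2 as written already faces it.

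**Conclusion.** The contradiction is real, narrow and minor. It concerns scheduled-ECG changes that are asymptomatic, non-serious and compatible with continued dosing, but that need altered care or, mainly, surveillance. Its main effect is on whether asymptomatic rhythm or morphology findings enter the AE tables. The conclusion assumes that the site takes the restrictive sentence in 6.3.3 at its word and follows the pointer in 6.3.8.1.

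A reader might infer more than the document supports:
- *That safety data are lost or the AE tables are unreliable.* The data are kept, and the protocol gives no rate for such findings. Counting scheduled ECGs would show how often the rules could apply, not how many events are at stake.
- *That only a label is affected.* This cannot be asserted while cardiac AE is undefined.
- *That volunteers will be withdrawn because of the conflict.* This depends on a reading of Section 3.2 that the protocol neither adopts nor excludes.
- *That the primary comparison is undermined.* Its method and the sample size are untouched. At most, a withdrawal under 3.2 could cost a volunteer's later periods.

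**What to change.** Make two changes together.

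1. In the restrictive sentence of Section 6.3.3, add a third condition for ECGs: the change is judged to call for altered volunteer care, surveillance or study participation, with a cross-reference to Section 11.1.2. The pointer in 6.3.8.1 then leads to the same rule and can stay. This direction is better than making 11.1.2 defer to 6.3.3, because the reason given in 6.3.3 for withholding the AE label does not cover paper ECGs.
2. In Section 3.2, state whether an ECG-only AE of this kind counts as a cardiac AE.

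The drafting cost is one clause and one sentence, handled as a protocol change under Section 8.5. The operational cost depends on the answer in item 2. If such an AE is not a cardiac AE, no procedure is added. If it is, each one brings the echocardiogram, repeat biomarkers, referral and unreplaced withdrawal described above, and the sponsor should choose that knowingly. If dosing has already begun, the abnormal paper ECGs in the eCRF need one check against the aligned rule before database lock.

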11.2 Calculation or derivation of pharmacokinetic variables

The PK analyses of the plasma concentration of AZD6244 amide will be performed. Pharmacokinetic analyses will be conducted according to the following procedures (SOPs) for PK analyses if not otherwise specified.

Pharmacokinetic parameters in plasma will be derived using noncompartmental methods with

Actual elapsed time from dosing will be used for final plasma PK parameter calculations. Pharmacokinetic parameter units will be consistent with the plasma concentration units specified in the bioanalytical data. No conversion of units will be made.

If data permits and unless otherwise stated, the following PK parameters will be determined for AZD6244, *N*-desmethyl AZD6244, and AZD6244 amide, following single-dose administration:

AUC	Area under the plasma concentration-time curve from zero to infinity (AUC, ng*h/mL), calculated by linear up/log down trapezoidal summation
-----	---------------------------------------------------------------------------------------------------------------------------------------------

$AUC_{(0-t)}$	Area under the plasma concentration-time curve from zero to the time of the last quantifiable concentration [$AUC_{(0-t)}$, ng*h/mL], calculated by linear up/log down trapezoidal summation
$AUC_{(0-12)}$	Area under the plasma concentration-time curve from zero to the time of 12 hours [$AUC_{(0-12)}$, ng*h/mL], calculated by linear up/log down trapezoidal summation
C_{max}	Maximum plasma concentration (C_{max} , ng/mL), obtained directly from the observed concentration versus time data
t_{max}	Time to C_{max} (t_{max} , h)
CL/F	Apparent oral plasma clearance (CL/F, L/h, AZD6244 only)
V_{ss}/F	Apparent volume at distribution equilibrium, $MRT*CL/F$ (V_{ss}/F , L, AZD6244 only)
V_z/F	Apparent volume of distribution (V_z/F , L, AZD6244 only)
$t_{1/2}$	Terminal half-life ($t_{1/2}$, h)
λ_z	Terminal rate constant (λ_z , 1/h).

Metabolite to parent drug ratios will be calculated for the primary PK parameters AUC and C_{max} .

The following PK parameters will be calculated for diagnostic purposes and listed, but will not be summarized:

- The time interval (h) of the log-linear regression to determine $t_{1/2}$ ($t_{1/2}$, interval)
- Number of data points ($t_{1/2}$, N) included in the log-linear regression analysis used to determine λ_z . A minimum of 3 data points will be used for λ_z determination
- Coefficient of determination for calculation of λ_z (Rsqr). The λ_z and related parameters will be reported only if Rsqr is 0.800 or more
- Percentage of AUC obtained by extrapolation (%AUC_{ex}); if the extrapolated area (%AUC_{ex}) is greater than 20% then AUC for that specific profile will not be reported

Pharmacokinetic parameters shall be computed and reported if the anomalous predose concentration value is not greater than 5% of the maximum observed concentration (C_{max}) in the profile. If the anomalous predose concentration value is greater than 5% of the maximum observed concentration (C_{max}) in the profile, PK parameters for the profile shall not be reported. If an anomalous concentration value is observed at the terminal phase and is judged as physiologically unreasonable, it will be excluded from computing parameter estimates.

Additional PK parameters may be calculated if deemed appropriate.

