The oral solution proposed for use in this study has not previously been administered to humans in a clinical study. The dose for use in study D1532C00066 was selected based upon preclinical experience of the solution performance in both dog and monkey and the bioavailability observed. The relative bioavailability of the capsule formulation compared to the Phase I AZD6244 free base in Captisol[®] suspension (“mix and drink”) was comparable in preclinical studies in dog and in a clinical study in patients (D1532C00005). Therefore the relative bioavailability of the oral solution to the capsule in dog was considered to be predictive of the expected performance in human and this was used to derive a suitable dose. This preclinical relative bioavailability predicted a potential for up to a 2-fold difference in exposure (both C_{max} and AUC), and this also took into account that the oral solution is not dissolution rate limited and a more rapid and complete absorption is possible, resulting in a higher C_{max} . Therefore, in order to minimize the risk of exceeding the mean AUC and C_{max} observed with a 75-mg dose of the AZD6244 capsule formulation, a solution dose of 35 mg (approximately half that of the capsule) was recommended.

For Dosing Period 1, 2 volunteers will receive AZD6244 doses at least 2 days before the remainder of the volunteers.

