5.5.2 Doses and treatment regimens

This study will consist of single oral AZD6244 doses administered either as a capsule formulation or as an oral solution as shown below. Treatment A and Treatment C will be administered on 1 occasion and Treatment B will be administered on 2 occasions.

- Treatment A will consist of three 25-mg AZD6244 white (current Phase II) capsules

- Treatment B will consist of three 25-mg AZD6244 blue (planned Phase III) capsules
- Treatment C will consist of 35-mg AZD6244 solution (administered as 35 mg in 50 g of solution)

The treatments will be given according to their randomized sequence. Volunteers will be required to fast from midnight before the day of dosing (Day 1) and should remain fasted until 4 hours after dosing. Water will be restricted up to 1 hour prior to dose through 1 hour postdose.

Oral doses of AZD6244 will be administered with approximately 240 mL water with the volunteer in an upright position. The capsules must be swallowed whole and not crushed, chewed, or divided.

The solution formulation will be administered with water to a total of approximately 240 mL water. The AZD6244 in 25% w/v aqueous Captisol[®] oral solution will have a weight of 50 g (ie, an approximately 50 mL volume) and volunteers will be provided with at least 190 mL water to rinse the container.

Refer to the Laboratory Handling Instructions for more information.

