12.2.2 Pharmacokinetic analyses

Pharmacokinetic blood sample collection times as well as derived sampling time deviations will be listed. Plasma concentration-time data (for AZD6244, *N*-desmethyl AZD6244 and AZD6244 amide) will be listed and summarized by treatment.

Data from volunteers excluded from the PK analysis population will be included in the data listings, but not in the summaries.

Pharmacokinetic variables will be summarized by treatment using appropriate descriptive statistics (eg, *n*, geometric mean, coefficient of variation [CV], minimum, median, and maximum) for all variables except t_{max} which will use *n*, arithmetic mean, standard deviation (SD), minimum, median, and maximum. The geometric mean is calculated as the exponential of the arithmetic mean calculated from data on a log scale.

The CV is calculated as:

$$100 \cdot \sqrt{(\exp(s^2) - 1)}$$

where s is the SD of the data on a log scale.

For descriptive statistics, concentrations below lower limit of quantitation (LLOQ) values will be handled as follows:

- At a time point where less than or equal to 50% of the values are below the LLOQ (BLQ), all BLQ values will be set to LLOQ, and all descriptive statistics will be calculated
- At a time point where more than half of the values are BLQ, the mean, SD, geometric mean and CV% will be set to 'not determined' (ND). The maximum value will be reported from the individual data, and the minimum and median will be set to BLQ
- If all values are BLQ at a time point, no descriptive statistics will be calculated for that time point. Not applicable (NA) will be written in the field for SD and CV%, and BLQ will be written in fields for mean, geometric mean, min, median, and max
- The number of BLQ values (n below LLOQ) will be reported for each time point.

Figures of arithmetic mean (\pm SD) plasma concentration-time data (for AZD6244, *N*-desmethyl AZD6244, and AZD6244 amide) up to 36 hours after the dose of each treatment period will be presented by treatment on both the linear and semi-logarithmic scales. Individual volunteer concentration-time data will be plotted on linear and semi-logarithmic scales.

Geometric mean and individual AUC and C_{\max} values will be presented by treatment. Graphical presentations of other PK data may be added at the discretion of the pharmacokineticist.

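### Vss/F is defined as MRT*CL/F although every dose is oral, so the reported volume contains an undisclosed absorption-time term and is overstated

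*Protocol*

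**What the plan says.** The synopsis lists Vss/F among the outcome variables for AZD6244. Section 11.2 gives its formula: "Apparent volume at distribution equilibrium, $MRT*CL/F". MRT is not defined there, is not in the parameter list and is not among the abbreviations. No adjustment for absorption time is stated.

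The method is noncompartmental ("Pharmacokinetic parameters in plasma will be derived using noncompartmental methods with"; the name of the software is missing from the text at hand). The route is oral throughout. Section 5.5.2: "This study will consist of single oral AZD6244 doses administered either as a capsule formulation or as an oral solution as shown below". There is no intravenous arm.

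On formulation, Section 3.3 says that "the oral solution is not dissolution rate limited and a more rapid and complete absorption is possible", and it adds on exposure: "This preclinical relative bioavailability predicted a potential for up to a 2-fold difference in exposure".

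On use, Section 12.2.2 says "Pharmacokinetic variables will be summarized by treatment using appropriate descriptive statistics". The same section confines inference to AUC (or AUC(0-t) as fallback) and Cmax.

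**The concern.** The formula MRT*CL gives the steady-state volume when MRT is the residence time of drug already in the circulation, as after an intravenous bolus. After an oral dose, the MRT obtained from the concentration curve also counts the time the drug spends dissolving and being absorbed. Multiplying that longer time by CL/F gives a quantity larger than the volume named in the label.

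This is a matter of what the protocol fixes, not of detail left for later: the formula is written out, and for an all-oral study it does not return the parameter it is said to define. What is at stake is the correctness of one listed outcome variable. There is a secondary risk that a later reader of the by-treatment summary takes a gap between solution and capsules as a difference in distribution when part of it reflects input speed.

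**Working it through.** **Identity.** For linear kinetics, with MRT(oral) = AUMC/AUC from the oral profile (the usual noncompartmental definition, assumed here because the protocol gives none):

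- MRT(oral) = MRT(disp) + MIT, where MIT is mean input time and MRT(disp) is the disposition MRT.
- Vss = MRT(disp) × CL.
- Hence MRT(oral) × CL/F = Vss/F + MIT × CL/F.
- Relative overstatement = MIT / MRT(disp).

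The term is positive whenever input is not instantaneous. The protocol states no value of MRT, Vss/F, half-life or clearance, so there is no planned figure to reproduce and every size below rests on assumed inputs.

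**Size, one compartment.** Here MRT(disp) = t1/2 / ln 2, so the overstatement is MIT × ln 2 / t1/2.

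| Assumed half-life | MIT 0.3 h | MIT 2 h |
|---|---|---|
| 5 h | 0.3 × 0.693 / 5 = 4.2% | 2 × 0.693 / 5 = 27.7% |
| 8 h | 2.6% | 17.3% |
| 12 h | 1.7% | 11.6% |

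The range is about 2% to 28%.

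**Does it appear under the planned sampling?** The check used the protocol's times ("Plasma samples will be collected predose and 0.5, 1, 1.5, 2, 4, 6, 8, 12, 24, and 36 hours postdose"), linear-up/log-down areas, and a terminal slope from the last three points. Two two-compartment parameter sets were assumed, each with true Vss 100 L, CL 12 L/h and F = 1, so MRT(disp) = 100/12 = 8.33 h.

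| MIT | Formula: 100 + 12 × MIT | Noncompartmental result, two sets |
|---|---|---|
| 0.25 h | 103 L | 107.0 and 105.2 L |
| 0.5 h | 106 L | 107.8 and 107.3 L |
| 1 h | 112 L | 113.3 and 113.3 L |
| 2 h | 124 L | 123.9 and 125.7 L |

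The planned sampling does not hide the term.

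**Between formulations, same true volume and same F.** The capsule/solution ratio is (MRT(disp) + MIT capsule) / (MRT(disp) + MIT solution). It was evaluated for MRT(disp) of 4, 6, 8 and 12 h and for solution/capsule MIT of 0.25/1, 0.5/1.5 and 0.5/2 h, all assumed:

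- Smallest: (12 + 1) / (12 + 0.25) = 1.06.
- Largest: (4 + 2) / (4 + 0.5) = 1.33.

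If white and blue capsules have the same MIT, their ratio is 1 and the term cancels from the comparison, although both values remain too high.

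**Effect of F.** Suppose capsule F is half of solution F, the extreme of the exposure difference in Section 3.3. With MRT(disp) 8 h and MIT 0.5/1.5 h, the ratio is (9.5 / 8.5) / 0.5 = 1.118 / 0.5 = 2.24. The factor 2.0 comes from F and only 1.12 from input time.

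**The case against.** The strongest reply is that nothing planned depends on Vss/F. It is summarized descriptively, no objective in Section 2 concerns distribution volume, and inference rests on AUC and Cmax. That stands in full and keeps the point minor.

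Second, Vss/F is an apparent parameter that already varies with F, and the F effect may be larger than the input-time effect, as the 2.24 example shows. That also stands: even a perfect MRT correction would not make solution and capsule values comparable as pure disposition. The same holds for Vz/F and CL/F. The difference is disclosure. The suffix /F tells the reader about bioavailability; nothing tells the reader about input time.

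Third, Section 11.2 defers to standard procedures where not otherwise specified, and an analysis plan not seen here could add a caveat on MRT. A caveat could sit there. A correction is much harder: the input term cannot be separated by noncompartmental methods from all-oral data. The formula itself is specified in the protocol.

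A reader might infer that Vss/F will differ between solution and capsules because of this term. The protocol does not support that. Section 3.3 calls more rapid absorption from the solution possible, on a preclinical prediction for a solution not previously given to humans. A reader might also infer that the term distorts the white-versus-blue comparison. Section 1.2 describes the capsule changes as minor with a low risk of a major effect on bioavailability, and the term largely cancels if absorption is similar. Finally, no section plans to interpret a Vss/F difference as a change in disposition.

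**Conclusion.** The definition is wrong as written. With oral dosing only and noncompartmental MRT, it returns Vss/F plus mean input time times CL/F, so the reported volume is too high in every profile. That conclusion is algebraic and needs only linear kinetics and MRT taken as AUMC/AUC.

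The size cannot be established from the protocol. It is about 2% to 28% under the stated one-compartment assumptions, which runs from negligible to moderate. The amount may, not must, differ between solution and capsules. The consequence is confined to one descriptive parameter; the AUC and Cmax comparisons, the between- and within-volunteer variability estimates and the sample size are untouched. It is worth correcting because the correction costs almost nothing.

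**What to change.** Preferred: delete Vss/F from Section 11.2 and from the outcome variables in the synopsis, with the matching abbreviation entry, and keep Vz/F, which is already listed and does not use MRT. Vz/F still depends on F, so it is not a formulation-free volume either. It also depends on the terminal slope: in the check above it stayed between 108.1 and 108.7 L in one parameter set but fell from 169.5 to 157.4 L (157.4 / 169.5 = 0.93) in the other as input time rose from 0.25 to 2 h.

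Alternative: keep Vss/F, define MRT in Section 11.2 and the abbreviations, and label the product wherever it is reported as uncorrected for input time and not for comparison across formulations.

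Cost: one descriptive parameter is lost or relabelled. No sample, visit, dataset or inferential analysis changes.
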